8.0 TOXICITIES TO BE MONITORED AND DOSAGE MODIFICATIONS

8.1 NCI Common Terminology Criteria for Adverse Events

This study will utilize the CTCAE (NCI Common Terminology Criteria for Adverse Events) Version 4.0 for toxicity and Serious Adverse Event reporting. A copy of the CTCAE Version 4.0 can be downloaded from the CTEP home page (http://ctep.cancer.gov). All appropriate treatment areas should have access to a copy of the CTCAE Version 4.0.

- 8.2 General Dose Modification Considerations
 - a. If multiple toxicities are experienced, dose modifications will be based on the toxicity requiring the largest dose reductions.
 - b. No dose escalation or re-escalation is allowed.
- 8.3 Dose Modifications for Dabrafenib, Trametinib, and GSK2141795

The table below outlines the dose levels to be used for any necessary dabrafenib, trametinib and GSK2141795 dose modifications:

Dose Level	Dabrafenib Dose/Schedule
0	150 mg BID
-1	100 mg BID
-2	75 mg BID
-3	50 mg BID

Dose Level	Trametinib Dose/Schedule
0	2 mg QD
-1	1.5 mg QD
-2	1.0 mg QD

Dose Level	GSK2141795 Dose/Schedule
0	75 mg QD
-1	50 mg QD
-2	25 mg QD

Dabrafenib, Trametinib, and GSK2141795 Dose Modification Guidelines

If an AE resolves to Grade 1 or baseline at the reduced dose level, and no additional toxicities are seen after 4 weeks of study treatment at the reduced dose, the dose may be increased to the previous dose level. A dose reduction below 50 mg BID for dabrafenib is not allowed. Dose reduction below 1 mg once daily for trametinib is not allowed. Dose reduction below 25 mg once daily for GSK2141795 is not allowed. However, if dabrafenib, trametinib, or GSK2141795 is permanently discontinued due to an agent specific toxicity (see below), the patient will be allowed to continue on the remaining agent(s).

Study Chair approval is required to restart study treatment after \geq 28 days of dose interruption.

The dose modifications may involve one or both agents, and should be based on the nature, severity and attributions of the AEs. General guidelines are provided in Tables below, with details stipulated in subsequent sections. Study Chair should be consulted if there are questions about the attribution of AEs and how the doses should be modified.

a. Dose Modification for Toxicities **Not Specified** in Subsequent Sections

	T	
CTCAE Grade	Action and Dose Modification	
Grade 1 Grade 2 (tolerable)	Continue study treatment at same dose level (no dose modification).	
	Monitor closely.	

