Subsequent Events:	 Clinical evaluation for infection and hypersensitivity^c Laboratory work-up^c Hydration as required^d Blood sample for cytokine analysis^e Within 3 days of onset of pyrexia: Optimize oral corticosteroid dose as clinically indicated for recalcitrant pyrexia.^g If corticosteroids have been tapered and pyrexia recurs, restart steroids. If corticosteroids cannot be tapered, consult medical monitor. 	 Interrupt dabrafenib. Continue trametinib and GSK2141795. Once pyrexia resolves to baseline, restart dabrafenib reduced by one dose level.^h If dabrafenib must be reduced to <50 mg BID, permanently discontinue dabrafenib.
h Dabrafenib should be reduced by one dose level after three episodes of pyrexia which cannot be managed by best supportive care and increasing doses of oral steroids. Escalation of dabrafenib is allowed if no episode of pyrexia is observed in the 4 weeks subsequent to dose reduction.	_	

c. Dose Modification for **Rash**

Rash is a frequent AE observed in patients receiving trametinib, dabrafenib, and GSK2141795.

The institutional standards for the management of skin-related AEs can differ from these guidelines. In this case, best clinical judgment should be applied and a consultation with the study chair or the CTEP Medical Monitor may be required.

Supportive Care and Dose Modification for Rash

CTCAE Grade	Adverse Event Management	Action and Dose Modification
Supportive care:		

Supportive care:

Prevention:

- Avoid unnecessary exposure to sunlight
- Apply broad-spectrum sunscreen (containing titanium dioxide or zinc oxide) with a skin protection factor (SPF) ≥15 at least twice daily.
- Use thick, alcohol-free emollient cream (e.g., glycerine and cetomacrogol cream) on dry areas of the body at least twice daily.
- Topical steroids and antibiotics should be applied at least twice daily starting on Day 1 of study treatment, to body areas such as face, chest, and upper back.

Use mild-strength topical steroid (hydrocortisone 1% cream) or topical antibiotic (e.g., clindamycin) or oral antibiotics (e.g., doxycycline 100 mg BID, minocycline 100 mg BID)

Action and Dose

2 weeks, interrupt study treatment until recovery to ≤

 Restart study treatment at reduced dose level (all

• Interrupt study treatment until

reduced by one dose level (all

rash recovers to ≤ grade 1.

Restart study treatment

 If no recovery to ≤ grade 2 within 28 days, permanently discontinue study treatment.

grade 1.

agents).3

agents).3,4

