Modification

Supportive Care and Dose Modification for Rash

Adverse Event Management

CTCAE Grade

Grade ≥3

Symptom management:		
Pruritic lesions: cool compresses and oral antihistamine therapies		
 Fissuring lesions: Mo 	nsel's solution, silver nitrate, or zir	nc oxide cream
Desquamation: thick	emollients and mild soap	
 Paronychia: antisepti 	c bath, local potent corticosteroids	s in addition to oral antibiotics; if no
improvement, consul-	t dermatologist or surgeon	
		iven systemic or topical antibiotics
*Rash prophylaxis is rec	ommended for the first 6 weeks of	study treatment
a. * Subjects who deve	lop rash/skin toxicities should be s	seen by a qualified physician and
_	ation for symptomatic/supportive	
Grade 1	Initiate prophylactic and	Continue study treatment.
	symptomatic treatment	If rash does not recover to
	measures.1	baseline within 2 weeks despite
	Use moderate strength topical	best supportive care, reduce
	steroid. ²	study treatment by one dose
	Reassess after 2 weeks.	level (all agents).3
Grade 2	Initiate prophylactic and	 Reduce study treatment by
	symptomatic treatment	one dose level.
	measures.1	 If rash recovers to ≤ grade 1
	Use moderate strength topical	within 2 weeks, increase dose to
	steroid. ²	previous dose level.
	Reassess after 2 weeks.	• If no recovery to ≤ grade 1 within

- 1. Rash prophylaxis is recommended for the first 6 weeks of study treatment.
- 2. Moderate-strength topical steroids: Hydrocortisone 2.5% cream or fluticasone priopionate 0.5% cream.

 Use moderate strength topical steroids PLUS oral methyl-

prednisolone dose pack.2

Consult dermatologist.

- 3. Approval of Study Chair is required to restart study treatment after >28 days of interruption.
- Study treatment may be escalated to previous dose level if no rash is evident 4 weeks after restarting study treatment.
 - d. Dose Modification for palmar-plantar erythrodysesthesia syndrome (PPES)
 - Lifestyle modification: avoidance of hot water, traumatic activity, constrictive footwear, or excessive friction on the skin and the use of thick cotton socks and gloves, and shoes with padded insoles

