Serum creatinine increase >0.2 mg/dL (18 mcmol/L) BUT ≤0.5 mg/dL (44 mcmol/L) above baseline	 Recheck serum creatinine within 1 week. Serum creatinine increase >1 week: contact CTEP Medical Monitor. If elevation persists beyond 4 weeks, recommend evaluation (consider renal biopsy) for etiology; consider nephrology consultation. If pyrexia is present, treat pyrexia as per guidelines.^a 	Continue study treatment at the same dose level.
Serum creatinine increase >0.5 mg/dL (44 mcmol/L) OR >2 mg/dL (>177 mcmol/L)	 Monitor serum creatinine ≥2-times per week. Hospitalization may be necessary if serum creatinine cannot be monitored frequently. If pyrexia is present, treat pyrexia per guidelines. Consult nephrologist if clinically indicated. Perform renal biopsy if clinically indicated, for example: Renal insufficiency persists despite volume repletion. Patient has new rash or signs of hypersensitivity (such as elevated eosinophil count). 	Interrupt study treatment until serum creatinine recovers to baseline. Restart study treatment.b

^a NSAIDs can induce renal insufficiency, especially in patients with dehydration; ;encourage oral fluids or consider IV fluids as clinically indicated. See guidelines for pyrexia Section 6.1.2.

j. Dose Modification for **Reduced Left Ventricular Ejection Fraction**

Decreases of the left ventricular ejection fraction (LVEF) have been observed in patients receiving trametinib. Therefore, ECHO/MUGA must be performed in regular intervals outlined in the Study Calendar. The same procedure (either ECHO or MUGA, although ECHO is preferred) should be performed at baseline and at follow-up visit(s).

^b Investigator may restart at either the same or a reduced dose level. Escalation of study treatment to previous dose level is allowed if another episode of renal insufficiency does not occur after 4 weeks of dose reduction. Consultation with the Study Chair is required before restarting study treatment if there is evidence of thrombotic microangiopathy.

Treatment Modification and Management Guidelines for LVEF Decrease

Clinic	LVEF-drop (%) or CTCAE grade	Dose Modification

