- a. Hypertension detected in two separate readings during up to three consecutive visits
- b. Well-controlled blood pressure defined as SBP ≤140 mm Hg and DBP ≤90 mm Hg in two separate readings during up to three consecutive visits.
- c. Escalation of trametinib to previous dose level can be considered if BPs remain well-controlled for 4 weeks after restarting of trametinib. Approval from Study Chair is required.
- d. Symptomatic hypertension defined as hypertension aggravated by symptoms (e.g., headache, light-headedness, vertigo, tinnitus, episodes of fainting) that resolve after the blood pressure is controlled within the normal range

I. Dose Modification for **QTc Prolongation and Valvular Changes**

Dose Modification for QTc Prolongation

QTc Prolongation ^a	Action and Dose Modification
• QTcB ≥501 msec	 Interrupt study treatment until QTcB prolongation resolves to grade 1 or baseline. Test serum potassium, calcium, phosphorus and magnesium. If abnormal, correct per routine clinical practice to within normal limits.
	Review concomitant medication usage for agents that prolong QTc.
	 If the event resolves, restart study treatment at current dose level^b. If the event does not resolve, permanently discontinue study treatment. Consider evaluation with cardiologist. If the event recurs, permanently discontinue study treatment. Consider evaluation with cardiologist.

Abbreviations: msec = milliseconds; QTcB = QT interval on electrocardiogram corrected using the Bazett's formula

- a) Based on average QTc value of triplicate ECGs. For example, if an ECG demonstrates a prolonged QT interval, obtain two or more ECGs over a brief period, and then use the averaged QTc values of the three ECGs to determine if study treatments should be interrupted or discontinued.
- b) If the QTc prolongation resolves to grade 1 or baseline, the subject may resume study treatment if the investigator and CTEP medical monitor agree that the subject will benefit from further treatment.

Dose modifications for valvular changes		

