Dabrafenib or Dabrafenib-Trametinib Treatment Modification and Management Guidelines for Diarrhea

- Calability 101 Digition		
CTCAE Grade	Management Guideline	ion and Dose Modification
Uncomplicated Diarrhea, ¹ Grade 3 or 4 Any Complicated Diarrhea ²	 Clinical evaluation mandatory. Loperamide³: Initially 4 mg, followed by 2 mg every 4 hours or after every unformed stool; maximum 16 mg/day. Continue until diarrhea-free for 12 hours. Oral antibiotics and second-line therapies if clinically indicated Hydration: Intravenous fluids if clinically indicated. Antibiotics (oral or intravenous) if clinically indicated. Intervention should be continued until the subject is diarrhea-free for ≥24 hours. Intervention may require hospitalization for subjects at risk of life-threatening complications. 	 Interrupt study treatment until diarrhea resolves to ≤ grade 1. Restart study treatment reduced by one dose level.⁴ If 3 dose reductions of study treatment are clinically indicated, permanently discontinue study treatment.

- 1. **Uncomplicated diarrhea** defined by the absence of symptoms such as cramping, nausea/vomiting, ≥ Grade 2, decreased performance status, pyrexia, sepsis, neutropenia ≥ Grade 3, frank bleeding, and/or dehydration requiring intravenous fluid substitution.
- 2. **Complicated diarrhea** defined by the presence of symptoms such as cramping, nausea/vomiting, ≥ Grade 2, decreased performance status, pyrexia, sepsis, neutropenia ≥ Grade 3, frank bleeding, and/or dehydration requiring intravenous fluid substitution.
- 3. Loperamide should be made available prior to start of study treatment so loperamide administration can begin at the first signs of diarrhea.
- 4. Escalation of study treatment to previous dose level is allowed after consultation with the medical monitor and in the absence of another episode of complicated or severe diarrhea in the 4 weeks subsequent to dose reduction.

n. Dose Modification for **Visual Changes**

Episodes of visual changes have been observed in patients receiving dabrafenib, trametinib, or the combination of both therapies. An ophthalmologist should be consulted if changes in vision develop. However, if the visual changes are clearly unrelated to study treatment (e.g., allergic conjunctivitis), then monitor closely as it may be reasonable to defer ophthalmic examination.

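### Section 8.2b bars all dose re-escalation, but Section 8.3 permits it in six places and the grade 2 rash row requires it

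*Combined protocol and SAP*

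**What the plan says.** Section 8.2b, among the general dose-modification considerations, states: "No dose escalation or re-escalation is allowed". It carries no exception and no cross-reference.

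Section 8.3 contains seven provisions that point the other way:

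- **General guideline, all three drugs.** If the adverse event has settled to grade 1 or baseline and no additional toxicity is seen "after 4 weeks of study treatment at the reduced dose, the dose may be increased to the previous dose level".
- **Pyrexia, note h (dabrafenib only).** "Escalation of dabrafenib is allowed if no episode of pyrexia is observed in the 4 weeks subsequent to dose reduction".
- **Rash, grade 2 row.** The dose is first cut by one level. If the rash then recovers to grade 1 or less "within 2 weeks, increase dose to" the previous level. The row is broken up in the extracted text, but all its words are there.
- **Rash, note 4 (marked on the grade 3 or higher row).** "Study treatment may be escalated to previous dose level if no rash is evident 4 weeks after restarting study treatment".
- **Renal insufficiency, note b.** "Escalation of study treatment to previous dose level is allowed if another episode of renal insufficiency does not occur" after 4 weeks of dose reduction.
- **Hypertension, note c (trametinib only, Study Chair approval required).** "Escalation of trametinib to previous dose level can be considered if BPs remain well-controlled for 4 weeks after restarting of trametinib".
- **Diarrhea, note 4.** "Escalation of study treatment to previous dose level is allowed after consultation with the medical monitor", provided there is no further complicated or severe episode in the 4 weeks after the reduction.

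Section 11.4 plans descriptive summaries of dose reductions, interruptions, discontinuations and the share of dose delivered, to assess safety and feasibility in both phases.

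**The concern.** A site that follows 8.2b keeps every dose reduction for the rest of treatment. A site that follows 8.3 may restore the dose after 4 weeks, and after grade 2 rash that recovers within 2 weeks it is told to. The dose a patient receives after a reduction therefore depends on which sentence the site reads.

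Because 8.2b names re-escalation as well as escalation, it cannot be read as only a cap on going above the starting dose. Section 8.3c describes rash as frequent with these drugs, so the one outright collision is not a remote case. What is at stake is the dosing of individual patients and the dose-delivery summary in 11.4.

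**Working it through.** **1. Can both rules be followed?**

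| 8.3 provision | Force | Can a site obey it and 8.2b? |
|---|---|---|
| General guideline | permits | Yes, by never using it |
| Pyrexia note h | permits | Yes, by never using it |
| Rash grade 2 row | directs | **No** |
| Rash note 4 | permits | Yes, by never using it |
| Renal note b | permits | Yes, by never using it |
| Hypertension note c | permits, with approval | Yes, by never using it |
| Diarrhea note 4 | permits, after consultation | Yes, by never using it |

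Six provisions are permissive: obeying 8.2b breaches none of them but makes all of them dead text. The seventh cannot be reconciled with 8.2b.

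**2. Effect on delivered dose, one dabrafenib step**

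Inputs: 150 mg BID reduced to 100 mg BID (8.3 dose-level table) and a 28-day cycle (7.5). Assumptions: cycle 1 at full dose, reduction at the start of cycle 2, interruption days ignored. Under 8.3, the dose is restored after exactly 4 weeks and never reduced again.

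- Full cycle: 56 × 150 = 8,400 mg. Reduced cycle: 56 × 100 = 5,600 mg. Difference: 2,800 mg, or 33.3%.
- Over n cycles under 8.2b: 8,400 + 5,600(n − 1). Under the 4-week rule: 8,400n − 2,800.
- Illustrative duration: Section 2.0 quotes a median PFS of 3.6 months for adding trametinib after progression on dabrafenib. 3.6 × 30.44 / 28 = 3.9, taken as 4 cycles.

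| Cycles | Planned (mg) | 8.2b | 4-week rule, at most |
|---|---|---|---|
| 3 | 25,200 | 19,600 = 77.8% | 22,400 = 88.9% |
| 4 | 33,600 | 25,200 = 75.0% | 30,800 = 91.7% |
| 6 | 50,400 | 36,400 = 72.2% | 47,600 = 94.4% |
| 12 | 100,800 | 70,000 = 69.4% | 98,000 = 97.2% |

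At 4 cycles the gap is 91.67 − 75.00 = 16.67 points. The grade 2 rash row can restore the dose sooner. If that happens at 2 weeks, 28 × 50 = 1,400 mg is lost and delivery is 32,200 / 33,600 = 95.8%.

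**3. Effect on the mean over 33 Phase II patients**

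The documents give no reduction rate, so the number reduced, k, is assumed. If every reduced patient is restored at 4 weeks, the mean gap is k/33 × 16.67:

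- k = 3: 1.5 points
- k = 5: 2.5 points
- k = 10: 5.1 points
- k = 15: 7.6 points

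These are upper bounds for each k under the 4-week rule. If only a fraction f is restored, the gap is multiplied by f. For k = 10 and f = 0.5 it is 10/33 × 16.67 × 0.5 = 2.5 points; for f = 0 it is zero.

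**4. One step for the other drugs, per cycle**

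- Trametinib 2 to 1.5 mg: 56 vs 42 mg (25%). 1.5 to 1 mg: 42 vs 28 mg (33%).
- GSK2141795 75 to 50 mg: 2,100 vs 1,400 mg (33%). 50 to 25 mg: 1,400 vs 700 mg (50%).

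**The case against.** The best defence is that specific rules override general ones, and that 8.3 tells sites to consult the Study Chair when unsure how to modify doses. Part of this stands. A specific-over-general reading would settle the five named toxicities, and the hypertension and diarrhea rules already pass through a central contact. But the protocol never states that order of precedence, and the opening guideline of 8.3 is itself general. For a reduction whose own table is silent on regaining dose, two general rules conflict and nothing decides between them. A site that reads only one of the two sentences sees a clear instruction and has no reason to ask.

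It is also fair to say that 8.3 re-escalation is mostly optional and conditional, and that 11.4 is descriptive and reports the dose actually given under either reading. Both points stand. They limit the size of the problem and are why the figures above are bounds, not forecasts.

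Three stronger readings are tempting but not supported:

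- *That sites dosed differently, or that the trial's inference is affected.* The documents contain no conduct data, and nothing in the two-stage response design depends on 8.2b.
- *That 7.3a is a further conflict of the same kind.* It lets Phase I D+G patients move up to the next GSK2141795 cohort level. That is not recovery from a toxicity reduction, and D+G does not go on to Phase II. It needs only a mention in the exception.
- *That pyrexia note h should lose its first sentence because it words the trigger for reduction more narrowly than its table cell.* The note is attached to the reduction instruction and can be read as its condition. Deleting the sentence would force a reduction after a third or later fever even when it was well managed. That is a clinical change the documents do not call for, and pyrexia notes a to g are missing from the extracted text.

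**Conclusion.** The inconsistency is real and lies in current text. 8.2b is wrong as written: it forbids what the general guideline and five toxicity rules of 8.3 allow, and what the grade 2 rash row requires. It deserves correction but is modest in weight.

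For one early dabrafenib step over 4 cycles, the two readings are at most 16.7 points of delivered dose apart under the 4-week rule. Over 33 patients the mean differs by at most 1.5 to 7.6 points for 3 to 15 reduced patients. These figures rest on an assumed duration, assumed reduction counts and prompt, lasting restoration in every reduced patient. Sample size, error rates and the response rule are untouched.

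**What to change.** Extend 8.2b so that "No dose escalation or re-escalation is allowed" is followed by: *except as stated in Section 8.3 (and, for Phase I D+G cohort escalation, Section 7.3a); where a toxicity table sets its own condition or approval for re-escalation, that condition applies.* The last clause preserves Study Chair approval for hypertension, medical monitor consultation for diarrhea and the 2-week trigger for grade 2 rash. It stops the general guideline from bypassing them.

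The edit is one line at the next amendment, but it is not neutral. It confirms that the general 8.3 guideline also covers reductions whose own tables do not mention regaining dose: unspecified toxicities, hemorrhage, LVEF decrease, valvular changes, RPED, uveitis and VTE. If the sponsor wants any of these reductions to be permanent, the relevant table should say so in the same amendment. That is a clinical decision, and it is the main cost of the change.

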Pneumonitis has been observed in patients receiving trametinib in combination with dabrafenib. To reduce the risk of pneumonitis, patients will be monitored closely for symptoms, evaluated with imaging and functional tests when appropriate.

	CTCAE Grade
Grade 1	
Grade 2	
Grade 3	
Grade 4	

p. Dose Modification for **Liver Chemistry Changes**

Dabrafenib or Dabrafenib-Trametinib Dose Modification for Liver Chemistry Changes

Dabrateriib of Babrateriib Traffictii	no Dose Modification for Liver Chemistry Changes
Event	Treatment modifications and assessment/monitoring
ALT ≥3x ULN but <5x ULN and TB <2x ULN, without symptoms considered related to liver injury or hypersensitivity and who can be monitored weekly for 4 weeks	 May continue study treatment. Report as SAE if CTEP-AERS reporting criteria is met. If liver chemistry stopping criteria are met any time, proceed as described below.
	MONITORING: Repeat LFT (ALT, AST, ALK, bilirubin) until they return to normal/baseline or stabilise (LFT may be every 2 weeks after 4 weeks if ALT <3x ULN and TB <2 ULN).
 Criteria for discontinuing study drug: When any of the liver stopping criteria below is met, discontinue trametinib and dabrafenib. 1. ALT ≥3xULN and bilirubin ≥2x ULN or >35% direct bilirubin^{1, 2} 2. ALT ≥ 3xULN and INR >1.5, if INR measured² (INR threshold does not apply if subject is on anticoagulant) 3. ALT ≥5x ULN 4. ALT ≥3x ULN persists for ≥4 weeks 	 Immediately discontinue study treatment. Do not restart/rechallenge unless approved by Study Chair. Report as SAE if: 1) CTEP-AERS reporting criteria are met, or 2) patients meet criteria 1-2. Perform liver event ASSESSMENT AND WORKUP (see below). Monitor the subject until liver chemistries resolve, stabilize, or return to baseline (see MONITORING below). If applicable, provide details on required follow up assessments (e.g., follow up for overall survival or disease recurrence or progression). MONITORING: In patients stopping for criteria 1-2 (with abnormal TB

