5. ALT ≥3x ULN and cannot be monitored weekly for 4 weeks 6. ALT ≥3x ULN associated with symptoms³ (new or worsening) believed to be related to liver injury or hypersensitivity	 In patients stopping for criteria 1-2 (with abnormal TB and INR, indicating potentially more significant liver toxicities): Repeat liver chemistries (ALT, AST, ALK, bilirubin) and perform liver event follow-up assessments within 24 hours. Monitor subjects twice weekly until LFT return to normal/baseline or stabilize. A specialist or hepatology consultation is recommended. In patients stopping for criteria 2-6: Repeat LFT and perform liver event follow up assessments within 24-72 hours Monitor subjects weekly until LFTs return to normal/baseline or stabilize. ASSESSMENT and WORKUP: Viral hepatitis serology.⁴ If possible, obtain blood sample for PK analysis.⁵ Serum CPK and LDH. Fractionate bilirubin, if total bilirubin ≥2x ULN.

Event	Treatment modifications and assessment/monitoring
(Contd.)	 CBC with differential to assess eosinophilia. Record clinical symptoms of liver injury, or hypersensitivity on AE CRF. Record concomitant medications (including acetaminophen, herbal remedies, other over the counter medications). Record alcohol use.
	 Additional work up for patient stopping for criteria 1-2 (with abnormal TB and INR, indicating potentially more significant liver toxicities): Anti-nuclear antibody, anti-smooth muscle antibody, Type 1 anti-liver kidney microsomal antibodies, and quantitative total immunoglobulin G (IgG or gamma globulins).
	 Serum acetaminophen adduct HPLC assay (in subjects with likely acetaminophen use in the preceding). If there is underlying chronic hepatitis B (e.g. positive hepatitis B surface antigen): quantitative hepatitis B DNA and hepatitis delta antibody.⁶ Liver imaging (ultrasound, MRI, CT) and /or liver biopsy.

Footnotes:

- Serum bilirubin fractionation should be performed if testing is available. If serum bilirubin fractionation testing is unavailable, record presence of detectable urinary bilirubin on dipstick, which indicates direct bilirubin elevations and suggesting liver injury.
- All events of ALT ≥3xULN and bilirubin ≥2xULN (>35% direct bilirubin) or ALT ≥3x ULN and INR >1.5 (if INR measured) may indicate severe liver injury (possible "Hy's Law"). INR measurement is not required, and the threshold value stated will not apply to subjects receiving anticoagulants.

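### D+T+G Phase I: a drug-related liver event that 8.3p flags as possible severe injury stops treatment and is an SAE, yet is not a DLT under 7.4c if it recovers within 7 days

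*Combined protocol and SAP*

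**What the plan says.** Section 7.4c lists five DLT types for D+T+G, limited to Cycles 1-2 and to drug-related events. They are febrile neutropenia; Grade 4 neutropenia lasting over 7 days; Grade 4 platelet decrease; Grade 3-4 rash, fever or hyperglycemia not recovered in 14 days; and (item 5) Grade 3-4 non-hematologic toxicity not recovered in 7 days. No liver-chemistry event is named.

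Section 8.3p sets six liver stopping criteria: "When any of the liver stopping criteria below is met, discontinue trametinib and dabrafenib". Restart is restricted: "Do not restart/rechallenge unless approved by Study Chair". Criteria 1 and 2 are singled out in two ways:

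- Reporting: "Report as SAE if: 1) CTEP-AERS reporting criteria are met, or 2) patients meet criteria 1-2".
- Monitoring: they are described as "indicating potentially more significant liver toxicities".

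Footnote 2 says that ALT at least 3x ULN with bilirubin at least 2x ULN (over 35% direct), or with INR above 1.5 if measured, "may indicate severe liver injury". Criterion 1 as printed is looser ("bilirubin ≥2x ULN or >35% direct bilirubin"). This point concerns only the footnote 2 event.

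Under 7.4b, 1 of 6 with a DLT means escalate, and 0-1 of 6 at Level 4 makes that level the MTD. Two or more stop enrollment at the level and send the study down. Patients without a DLT who fall short of the minimum exposure are not evaluable and are replaced.

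**The concern.** The DLT count drives each escalation step and the MTD. Section 8.3p makes the patient stop drug as soon as the event is seen, so early recovery may show only that withdrawal worked, not that the dose was tolerated. Yet early recovery is what takes the event out of item 5. An event that the protocol itself treats as possible severe liver injury can then be scored as no DLT, and the cohort can pass on a count one lower than its clinical experience.

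The organ is a plausible target. Section 2.0 reports AST elevation in 22% (Grade 3/4 in 9%) with trametinib plus GSK2141795. That is not a rate for the footnote 2 event, and the documents give none.

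**Working it through.** **1. The plan's boundary.** 1/6 = 16.7% and 2/6 = 33.3%. Section 7.4a requires DLT incidence below 33%, and 11.3 requires at most 33%. On either wording 1/6 is acceptable and 2/6 is not, which agrees with the 7.4b rules.

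**2. Does the event enter the count?** Items 1-4 of 7.4c do not describe it. Item 5 fails if recovery comes within 7 days. Nothing in 7.4b, 8.3p, 11.3 or 15.2 converts a stopping criterion or an SAE into a DLT.

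**3. Is the patient evaluable?** The Phase I calendar (9.2) draws ALT and bilirubin at Weeks 1, 3, 5, 7 and 9. PK blood falls in Weeks 3 and 5 and is due before dosing on Days 15 and 29, so Week 3 is Day 15. Uninterrupted dosing to that visit gives 14 days of drug. 14/28 = 50% of Cycle 1 dabrafenib and trametinib, and 14 exceeds the required 11 days of GSK2141795. The patient is therefore evaluable and DLT-free.

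**4. The decision.** With one other DLT in the cohort, the written count is 1/6: escalate, or MTD at Level 4. Counting the liver event in a different patient gives two DLTs: stop and go down.

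**5. How often.** Let p be the listed-DLT rate and h the rate of uncounted footnote 2 events, both assumed, with no overlap. Among patients without a listed DLT the event rate is q = h/(1-p).

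- A. Misread 1/6, intermediate level: 3p(1-p)^5 [1-(1-q)^5]
- B. Misread 1/6, Level 4: 6p(1-p)^5 [1-(1-q)^5]
- C. Pass, intermediate: (1-p)^3 + 3p(1-p)^5
- D. Pass, Level 4: (1-p)^6 + 6p(1-p)^5

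C and D are evaluated at p as written and at p+h if the event is counted. At p = 0.25, 3p(1-p)^5 = 0.178 and 6p(1-p)^5 = 0.356.

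| h | q | 1-(1-q)^5 | A | B | C at p+h | D at p+h |
|---|---|---|---|---|---|---|
| 0 (as written) | – | – | – | – | 0.600 | 0.534 |
| 0.1% | 0.0013 | 0.0066 | 0.12% | 0.24% | 0.598 | 0.532 |
| 0.5% | 0.0067 | 0.0329 | 0.6% | 1.2% | 0.589 | 0.522 |
| 1% | 0.0133 | 0.0649 | 1.2% | 2.3% | 0.578 | 0.510 |
| 3% | 0.0400 | 0.1846 | 3.3% | 6.6% | 0.536 | 0.464 |

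For h = 0.1-3%, A is 0.1-3.3% at p = 15% and 0.1-3.0% at p = 30%, so the result depends mainly on h.

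**6. A second effect.** An intermediate cohort can escalate on 0/3 when counting the event would have expanded it to six: (1-p)^3 [1-(1-q)^3]. At p = 0.25 this is 0.2% (h = 0.1%) to 4.9% (h = 3%).

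**The case against.** **The window is narrow.** The event must meet footnote 2, be drug-related, fall in Cycles 1-2 and recover within 7 days. Section 3.3 gives trametinib a half-life of 5.3 days, so 2^(-7/5.3), about 40%, remains a week after stopping, and quick recovery is not assured. Section 7.4c does not define recovery. If it means return to Grade 1 or baseline, as in the general dose-modification table, fewer events escape. This stands, and it is why h must extend well below 1%. The agent lists in section 3 point the same way: raised bilirubin appears for dabrafenib and trametinib only under insufficient evidence, and not at all for GSK2141795.

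**Stopping rules and DLTs serve different purposes.** Retinal vein occlusion also forces permanent trametinib discontinuation and an SAE report without being a named DLT. This is fair, and it makes the matter a design choice. But items 1 and 3 already count with no recovery clause, so the plan accepts that some events are limiting however fast they resolve.

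**Safeguards exist.** Adverse events are reported every 14 days, mandatory calls take place twice a month and feed selection of the Phase II dose (11.6, 15.2), and a temporary closure precedes Phase II. The event, as an SAE, will reach those people. They may act on it, but the written count is unchanged.

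**Stronger readings the documents do not support.** A reader might infer that such patients are routinely replaced and the event lost. Step 3 shows that this needs an unscheduled draw before Day 15 or missed doses, so it is a minor route. A reader might also infer that the event escapes by being below Grade 3. That rests on CTCAE cut-offs the documents do not print.

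**Conclusion.** The point holds as a gap in the written rule. A drug-related footnote 2 event in Cycles 1-2 that recovers within 7 days forces discontinuation and an SAE report but does not count toward dose selection. With one other DLT it changes the action from stop to escalate, or to declaring the MTD at Level 4.

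The effect is small. At p = 25% and h = 0.1-3% the misread count arises in about 0.1-3.3% of intermediate cohorts and 0.2-6.6% at Level 4. Counting the event would move pass probability from 0.600 to between 0.598 and 0.536 (Level 4: 0.534 to between 0.532 and 0.464). These figures assume no overlap between event types, evaluable patients, and rates that have no anchor in the documents. The rule conflict itself needs no rate.

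A reader might conclude that the escalation design is unsafe or that all six stopping criteria should be DLTs. Neither follows: the calls and the closure allow an override, and 8.3p singles out only criteria 1 and 2. This is a cheap improvement worth considering.

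**What to change.** Add one item to 7.4c: drug-related ALT at least 3x ULN with total bilirubin at least 2x ULN (over 35% direct where fractionation is available) in Cycles 1-2, regardless of grade or recovery time. If baseline ALT or bilirubin is above ULN, the value must also be at least 2x baseline. Count the INR criterion only if INR was measured and the patient is not on anticoagulants.

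The baseline clause is needed because 5.1n admits ALT up to 5x IULN with liver metastases and bilirubin up to 2.5x ULN with Gilbert's syndrome. The 2x multiple is a proposal that the study team should confirm in advance. Item 5 keeps its 7-day clause for isolated transaminase rises, and section 8 management is unchanged. Section 7.3c needs the same line only if D+G is still enrolling.

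The bilirubin arm needs no new test: ALT and bilirubin are already drawn every two weeks, and 8.3p already says "Fractionate bilirubin, if total bilirubin ≥2x ULN". The INR arm will apply unevenly, since "INR measurement is not required".

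The cost is a slightly higher chance of cohort expansion or a lower MTD. At p = 25% and h = 3%, the top of the assumed range, pass probability falls by about 6 points at an intermediate level (0.600 - 0.536) and 7 at Level 4 (0.534 - 0.464).
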